## 9.2 Power calculations for safety for Part B

The goal of the safety evaluation for Part B is to identify safety concerns associated with vaccine administration in Groups 2, 3, and 4. The ability of the study to detect SAEs can be expressed by the true event rate above which at least 1 SAE would likely be observed and the true event rate below which no events would likely be observed. Specifically, for each group in Part B ( $n = 12$ ), there is at least a 90% chance of observing at least 1 event if the true rate of such an event is 17.5% or more; and there is at least a 90% chance of observing no events if the true rate is 0.87% or less. For two vaccine groups of Part B combined (eg, Groups 2 and 3;  $n = 24$ ), there is a 90% chance of observing at least 1 event if the true rate of such an event is 9.2% or more; and there is a 90% chance of observing no events if the true rate is 0.43% or less. For all three vaccine groups of Part B combined ( $n = 36$ ), there is a 90% chance of observing at least 1 event if the true rate of such an event is 6.2% or more; and there is a 90% chance of observing no events if the true rate is 0.29% or less. For the four vaccine groups of Parts A and B combined ( $n = 48$ ), there is a 90% chance of observing at least 1 event if the true rate of such an event is 4.7% or more; and there is a 90% chance of observing no events if the true rate is 0.21% or less.

Binomial probabilities of observing 0, 1 or more, and 2 or more events among the 12 participants of each group (Groups 2, 3, or 4) are presented in Table 2-1 for a range of possible true AE rates. Binomial probabilities of observing 0, 1 or more, and 2 or more events among the 36 participants of Groups 2, 3, and 4 combined are presented in Table 2-3 for a range of possible true AE rates. These calculations provide a more complete picture of the sensitivity of this study design to identify potential safety problems with the vaccine.

**Table 2-3 Probability of observing 0 events, 1 or more events, and 2 or more events, among groups of 12, 24, 36, and 48 study participants for different true event rates**

True event rate (%)	group size	0 events	1+ events	2+ events
1	12	0.89	0.11	0.01
4	12	0.61	0.39	0.08
10	12	0.28	0.72	0.34
20	12	0.07	0.93	0.73
30	12	0.01	0.99	0.91
1	24	0.79	0.21	0.02
4	24	0.38	0.62	0.25
10	24	0.08	0.92	0.71
20	24	0.005	1.00	0.97
30	24	0.000	1.00	1.00
1	36	0.70	0.30	0.05
4	36	0.23	0.77	0.43
10	36	0.02	0.98	0.89
20	36	0.00	1.00	1.00
30	36	0.00	1.00	1.00
1	48	0.62	0.38	0.08
4	48	0.14	0.86	0.58
10	48	0.01	0.99	0.96
20	48	0.00	1.00	1.00
30	48	0.00	1.00	1.00

An alternative way of describing the statistical properties of the study design is in terms of the 95% confidence interval for the true rate of an AE based on the observed data. Table 2-4 shows the 2-sided 95% confidence intervals for the probability of an event based on a particular observed rate in one group (eg, Group 2, or 3, or 4; n = 12), or 2 groups (eg, Groups 2 and 3; n = 24), or 3 groups

(Groups 2, 3, and 4; n = 36), or 4 groups (Groups 1 through 4; n = 48). Calculations are done using the score test method for confidence interval described in Agresti and Coull formula 2 (44). If none of the 48 participants receiving any the study vaccines experience a safety event, the 95% 2-sided upper confidence bound for the true rate of such events in the total vaccinated population is 7.4%.

**Table 2-4 Two-sided 95% confidence intervals for the probability of observing a safety event based on observing a particular rate of safety endpoints in n = 12, or n = 24, or n = 36, or n = 48 study participants**

Observed event rate	95% Confidence interval (%)
---------------------	-----------------------------

0/12	[0.0 ; 24.2]
1/12	[1.5 ; 35.4]
2/12	[4.7 ; 44.8]
0/24	[0.0 ; 13.8]
1/24	[0.7 ; 20.2]
2/24	[2.3 ; 25.8]
0/36	[0.0 ; 9.6]
1/36	[0.5 ; 14.2]
2/36	[1.5 ; 18.1]
0/48	[0.0 ; 7.4]
1/48	[0.4 ; 10.9]
2/48	[1.2 ; 14.0]

## 10 STATISTICAL ANALYSIS

This section describes the final study analysis, unblinded as to treatment arm assignment. All data from enrolled participants will be analyzed regardless of how many vaccinations they received. All analyses will be performed using SAS and/or R.

### 10.1 Baseline demographics

Participants' baseline characteristics will be summarized using descriptive statistics.

### 10.2 Safety Analyses

**Reactogenicity:** The number and percentage of subjects experiencing each type of reactogenicity sign or symptom will be tabulated by severity. For a given sign or symptom, each subject's reactogenicity will be counted once under the maximum severity for all assessments. Onset date is the first date when symptom grade is mild or higher. If the resolution form with resolution date filled is submitted for a given symptom, then report the resolution date on this form. But if there is no resolution form nor any date in the resolution form then the resolution date is computed as the first date with grade "None" after "the maximum severity grade" and stays grade "None" for the remainder of the reporting period.

**Adverse Events:** AEs will be coded into Medical Dictionary for Regulatory Activities (MedDRA) preferred terms. The number and percentage of subjects experiencing each specific AE will be tabulated by severity and relationship to study vaccine. For the calculations in these tables, each subject's AE will be counted once under the maximum severity or strongest recorded causal relationship to treatment. A complete listing of AEs for each subject will provide details including severity, relationship to treatment, onset, duration and outcome.

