## 9 Safety and adverse events

### 9.1 Adverse events

Unsolicited AEs will be collected over a period of 30 days after each vaccination. All collected AEs are captured in the clinical database on the appropriate CRF. Clinic staff should evaluate every AE to determine if (1) the AE meets the requirements for expedited reporting (see Section 9.2.1), (2) if the AE meets the criteria for a safety pause/prompt AE review (see Section 9.7), (3) if the AE meets the criteria for an MAAE, and (4) if the AE is a potential immune-mediated disease that may be listed as an AE of special interest (AESI). A sample list of AESIs is provided in [Appendix H](#).

In addition, a limited set of AEs will be collected and reported for 12 months following the any vaccine administration

- SAEs/EAEs,
- AESIs,
- MAAEs (defined as any adverse events leading to an unscheduled visit to a healthcare professional)
- AEs leading to early participant withdrawal or early discontinuation of study vaccine(s) administration.

Adverse events (AEs) will be graded according to the Division of AIDS (DAIDS) Table for Grading the Severity of Adult and Pediatric Adverse Events, Corrected Version 2.1 (<https://rsc.niaid.nih.gov/clinical-research-sites/daids-adverse-event-grading-tables>), with the following exceptions:

- Unintentional Weight Loss is required to be reported as an AE only if it is considered to be potentially deleterious to the participant's health (see HVTN 300 SSP);
- Creatinine is required to be reported as an AE only if it is gradable per the increase from local lab ULN parameter. Do not grade elevated creatinine based on the change from the baseline parameter.
- Do not grade creatinine clearance or eGFR based on the change from the baseline parameter. Do not grade on the basis of eGFR if there is clinical concern for kidney injury.

- Injection Site Erythema or Redness and Injection Site Induration or Swelling will not consider surface area and interference with usual social and functional activities such that:
  - Grade 1 is: 2.5 to < 5 cm in diameter;
  - Grade 2 is:  $\geq 5$  to < 10 cm in diameter;
  - Grade 3 is:  $\geq 10$  cm in diameter OR Ulceration OR Secondary infection OR Phlebitis OR Sterile abscess OR Drainage;
  - Grade 4 is: Potentially life-threatening consequences (eg, abscess, exfoliative dermatitis, necrosis involving dermis or deeper tissue);

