#### *Primary endpoint 3:*

Local and systemic reactogenicity signs and symptoms will be collected for a minimum of seven days following receipt of any study vaccine.

Serious adverse events (SAEs), medically attended adverse events (MAAEs), adverse events of special interest (AESIs) and AEs leading to early participant withdrawal or permanent discontinuation which will be collected throughout the study and for twelve months following any receipt of study product. Additionally, all adverse events will be collected for 30 days after any receipt of study vaccination.

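### The SAP's adverse event tables set no onset window, so each percentage mixes all AEs from the 30-day post-dose periods with only the qualifying AEs from the rest of follow-up

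*SAP*

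**What the plan says.** **Collection.** Protocol 9.1 sets two rules. For ordinary events, "Unsolicited AEs will be collected over a period of 30 days after each vaccination". Separately, "a limited set of AEs will be collected and reported for 12 months following the any vaccine administration": SAEs/EAEs, AESIs, MAAEs, and AEs leading to withdrawal or to stopping study vaccine. Primary endpoint 3, repeated in SAP 4, has the same split: "all adverse events will be collected for 30 days after any receipt of study vaccination", and for the limited set, "which will be collected throughout the study and for twelve months following any receipt of study product". The schedules in Protocol Appendices A and B agree. The general AE row ends at Visit 11 (Day 378), while the AESI/MAAE/SAE row runs on to Visit 12 (Day 560) and the AESI contact (Day 728).

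An MAAE is any AE that leads to an unscheduled visit to a healthcare professional, so any preferred term can qualify. Both streams are recorded together: "All collected AEs are captured in the clinical database on the appropriate CRF."

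**Analysis.** SAP 10 states: "All data from enrolled participants will be analyzed regardless of how many vaccinations they received." SAP 10.2 then plans: "The number and percentage of subjects experiencing each specific AE will be tabulated by severity and relationship to study vaccine." Each participant is counted once, at maximum severity or strongest relationship. The tables by body system and preferred term in SAP 11.1 carry no onset window. EAEs/SAEs have their own table. MAAEs and AESIs appear only as listings (SAP 11.1 and 11.2). AEs leading to withdrawal or discontinuation have no table of their own.

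**The concern.** A percentage of participants with an event can be interpreted only if the reader knows over what time the event was looked for. Here ascertainment changes part-way through each participant's follow-up. A headache on day 20 after a dose is recorded whether or not the participant sees anyone about it. A headache on day 45 after a dose is recorded only if it led to an unscheduled visit or otherwise qualified for the limited set. If both go into the same row, the result is neither the 30-day frequency of all AEs nor the whole-follow-up frequency of qualifying AEs.

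Two features unrelated to the product's safety then affect the figure: how readily participants seek care between doses, and how many doses they received. A participant whose vaccinations stop early counts fully in the denominator but has fewer 30-day periods in which ordinary AEs are sought. These tables summarise part of a primary endpoint, so the quantity they show should be defined.

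**Working it through.** **The plan's own figures.** SAP 9 gives no figure for this point. Its stated safety figures do reproduce: for n = 12, 1 − (1 − 0.175)^12 = 0.901 and (1 − 0.0087)^12 = 0.900, and the score upper bound for 0/12 is 24.2%. Nothing below depends on them.

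**Days in each window.** Doses fall on Days 0, 56, 112, 224 and 364 (schema), and the last contact is on Day 728 (Appendices A and B).

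- On schedule, the shortest gap between doses is 56 days, so the 30-day windows do not overlap.
- In-window days: 5 × 30 = 150. Share of follow-up: 150/728 = 20.6%.
- Off-window days: 728 − 150 = 578, open only to the limited set.
- The visit windows in Appendix C could bring dose 2 (Day 70 at latest) and dose 3 (Day 91 at earliest) to 21 days apart, an overlap of 9 days. This is ignored here.

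**Fewer doses.** Follow-up is taken to 364 days after the last dose.

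| Doses received | In-window days | Follow-up days | Share |
|---|---|---|---|
| 1 | 30 | 364 | 8.2% |
| 2 | 60 | 420 | 14.3% |
| 3 | 90 | 476 | 18.9% |
| 4 | 120 | 588 | 20.4% |
| 5 | 150 | 728 | 20.6% |

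**Effect on a percentage (illustration).** Let a preferred term occur at a constant rate λ per person-year, and let a share m of off-window events be captured, taken here as medically attended. Neither λ nor m is in the documents; both are assumptions.

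- All AEs within 30 days of a dose: 1 − exp(−λ × 150/365.25)
- Pooled, as the SAP reads: 1 − exp(−λ × (150 + 578m)/365.25)
- Qualifying AEs over all follow-up: 1 − exp(−λ × m × 728/365.25)

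With m = 20%, 150 + 578 × 0.2 = 265.6 days:

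| λ per year | 30-day, all AEs | Pooled | Qualifying only, all follow-up |
|---|---|---|---|
| 0.25 | 9.8% | 16.6% | 9.5% |
| 0.5 | 18.6% | 30.5% | 18.1% |
| 1 | 33.7% | 51.7% | 32.9% |

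Sensitivity to m at λ = 0.25: for m from 10% to 50% the pooled figure runs from 13.3% to 26.0%, against a fixed 9.8% for the 30-day figure and 4.9% to 22.1% for qualifying events. Off-window events make up 28% to 66% of the events counted. At m = 0 the pooled figure equals the 30-day figure. At m = 100% it equals the whole-follow-up figure (39.2%).

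**Effect of one early stop (illustration).** Let q be the assumed chance of an ordinary AE in one 30-day window, independent across windows. Five doses give 1 − (1 − q)^5; one dose gives q.

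- q = 5%: 22.6% against 5%. One such participant in 12 lowers the group figure by (22.6 − 5)/12 = 1.5 percentage points.
- q = 10%: 41.0% against 10%, or 2.6 points.
- q = 20%: 67.2% against 20%, or 3.9 points.

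**The case against.** **The mixing is inferred from silence.** No sentence in the SAP says that off-window MAAEs are pooled with 30-day AEs. Endpoint 3 states what is collected and for how long, not what percentage is to be reported. The table shells are not in these documents and may apply a window. This stands as a qualification. But the SAP says all data are analysed, and if a window is intended, the SAP is where it should be stated.

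**Much is already recoverable.** EAEs/SAEs have their own table. AESIs and MAAEs are listed. A complete AE listing carries onset. A related-only table is planned, and it should filter out much of the background illness in the illustration. Dosing frequencies and protocol status are tabulated alongside. With 12 participants per group, a reader could count either window by hand. All of this stands and limits the importance of the point; it does not supply a defined percentage.

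**Stronger readings that the documents do not support.**

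- *That the tables never match either window.* A term with no qualifying off-window events equals its 30-day percentage, and one whose off-window events all qualify equals its whole-follow-up percentage.
- *That the comparison of adjuvant regimens is biased towards the less tolerated one.* All groups share one dosing schedule and the same collection rules, so pooling tends to raise every group's figures. It distorts a comparison only if care-seeking or stopping differs between groups, and nothing in the documents shows that. The rationale for the 3 mcg dose (Protocol 2.5) rests on reactogenicity, which has separate tables and figures. SAP 7 already calls for caution in comparing non-randomised groups.
- *That the plan expects about 2 of 12 to stop vaccination, from its 17%.* Protocol 6.1 gives that figure as a rate of missing immunogenicity data, including shipping problems and assay background. Protocol 6.1.1 applies it to loss before an immunogenicity time point. The documents give no rate of stopping vaccination.

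**Restricting every table to 30 days would hide late-onset events.** This is a fair objection to a blanket restriction in a first-in-human trial with 12-month follow-up. The fix therefore leaves the severe and related-only tables over all follow-up.

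**Conclusion.** The point holds as a minor reporting gap. As written, SAP 10.2 and 11.1 give AE percentages with no onset window, although ascertainment covers all AEs on 150 of 728 days and only four classes of AE on the other 578. Apart from the two extremes, such a percentage corresponds to neither collection window of primary endpoint 3 and moves with care-seeking and doses received.

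Under assumed rates of 0.25 to 1 episode per person-year with 20% medically attended, the 30-day figure is 10% to 34% and the pooled figure 17% to 52%. These sizes rest on a constant rate, on-schedule dosing and an assumed attended share. Only the window lengths come from the documents. Sample size, data collection and the reactogenicity tables are unaffected.

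**What to change.** In SAP 10.2 and 11.1:

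1. Present the all-AE tables (by body system, and by preferred term for all severities and for any relationship) for AEs with onset within 30 days after a dose. Beside the percentage of participants, show the number of events per vaccination administered, so that early stopping is visible.
2. In the Final Study Report, add counts and percentages over the whole follow-up for MAAEs, AESIs and AEs leading to withdrawal or discontinuation. Keep the existing EAE/SAE table.
3. Keep the table of severe, life-threatening or fatal events and the related-only table over all follow-up, with a flag for onset inside or outside the 30-day window.
4. State the onset window in each table title.

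The cost is SAP wording and a few more tables, built from onset dates that are already collected. No new data are needed.

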**Table 2-2 Ongoing studies with HIV Env trimers**

Protocol	Immunogen	Dose (N), route	Adjuvant	Schedule	Safety data (related)
HVTN 122	gp145 C.6980 (oligomers, > 50% trimer)	300 mcg (25) 100 mcg (15) IM	Alum (500 mcg)	Month 0, 2, 6	No SAEs One Grade 3 induration No product- associated early terminations
IAVI W001 (NCT03699241)	BG505 SOSIP.664	30 mcg (20) 100 mcg (20) 300 mcg (10) IM	AS01 B	Month 0, 2, 6	No SAEs No Grade 3 or 4 AEs No Early Terminations
HVTN 137 (Part A)	BG505 SOSIP.664	100 mcg + 1 mcg 3M-052- AF+Alum (5), IM 100 mcg + 5 mcg 3M-052- AF+Alum (10), IM	3M-052-AF (1 or 5 mcg) + Alum (500 mcg)	Month 0, 2, 6 (optional)	No related SAEs or AESIs Two Grade 3 Local Reactogenicity Erythema/Induration Two early terminations
HVTN 137 (Part B, Group 4)	BG505 SOSIP.664	100 mcg (20), IM	5 mcg 3M- 052-AF + 500 mcg Alum	Month 0, 2, 6	No related SAEs or AESIs
HVTN 300 (Part A)	CH505 TF chTrimer	300 mcg (12), IM	3M-052-AF (5 mcg) + Alum (500 mcg)	Month 0, 2, 4, 8, 12	No related SAEs, AESIs

**HVTN 122:** The gp145 C.6980 immunogen is an HIV Env trimer developed by the United States Military HIV Research Program (MHRP), constructed with modifications to facilitate trimer assembly. The safety and immunogenicity of the predominantly trimeric gp145 C.6980 was evaluated in HVTN 122 at 100 mcg and 300 mcg protein dose admixed intramuscularly with aluminum hydroxide adjuvant (months 0, 2, 6). While analysis of the trial data is still ongoing, no serious adverse events related to study product administration were reported. HVTN 122 is closed and no early terminations associated with an adverse event deemed related to study product have been reported. There has been one report of Grade 3 induration. No related SAEs have been reported. 60% (n=27) of participants experienced one or more AEs, of which only one AE (mild injection site pruritis) was deemed related to study product.

**IAVI W001:** BG505 SOSIP.664 gp140, the native-like stabilized SOSIP trimer sharing the gp41 sequence and highly similar biophysical and antigenicity properties with the CH505 TF chTrimer (12, 13). This immunogen is currently being evaluated in IAVI W001 (NCT03699241), a randomized double-blinded, placebo-controlled, dose-escalation Phase 1 clinical trial evaluating safety and immunogenicity of recombinant HIV BG505 SOSIP.664 gp140 vaccine

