### 9.3.2 HVTN Safety Monitoring Board (SMB)

The SMB is a multidisciplinary group consisting of biostatisticians, clinicians, and experts in HIV vaccine research that, collectively, has experience in the conduct and monitoring of vaccine trials. Members of the SMB are not directly affiliated with the protocols under review.

The SMB reviews safety data (including cumulative reactogenicity events, AEs, laboratory safety data, and individual SAE reports) approximately every 4 months. The SMB conducts additional special reviews at the request of the HVTN 300 PSRT.

Study sites will receive SMB summary minutes and are responsible for forwarding them to their IRB/EC and any applicable Regulatory Entity.

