## **5 COHORT DEFINITION**

Recruitment will target enrolling a total of 48 healthy, HIV-uninfected adult participants in 4 groups.

In Part A, recruitment will target enrolling 12 healthy, HIV-uninfected adult participants in Group 1. The protocol team will convene after the 12th participant has received their third vaccination to

determine if further participants should be enrolled to evaluate immunogenicity. Examples of reasons that might necessitate enrollment of additional participants are provided in Section 1.5. If some participants from the original number of 12 enrolled will not contribute data to some of the immunogenicity analyses, the protocol team may enroll additional fully evaluable participants, up to 6 additional participants, or a total of 18 participants enrolled, with the goal of at least 12 contributing to the final immunogenicity analyses.

In Part B, recruitment will target enrolling a total of 36 healthy, HIV-uninfected adult participants in Groups 2, 3, and 4 ( $n = 12$  participants per group). Enrollment in Groups 2, 3, and 4 will be stepwise by group, starting with Group 2, continuing with Group 3, and finishing with Group 4.

Since enrollment is concurrent with receiving the first study vaccination, all participants will provide some safety data.

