## 11 SAFETY TABLES, PARTICIPANT LISTINGS, AND FIGURES

### 11.1 List of Tables

The following tables are included in the SMB reports and FSR for safety:

- Enrollment Report
- Demographics and Study Product Administration Frequencies
- Overall Protocol Status
- Maximum Local and Systemic Reactogenicity Summaries
- Adverse Experiences by Body System and Severity – By Decreasing Frequency
- Adverse Experiences by Preferred Term and Severity – By Decreasing Frequency – Includes Severe, Life-threatening or Fatal Experiences Only
- Adverse Experiences by Preferred Term and Severity – By Decreasing Frequency – Includes Experiences of All Severities
- Adverse Experiences by Preferred Term and Relationship to Study Product – By Decreasing Frequency – Includes Related Experiences Only
- Adverse Experiences by Preferred Term and Relationship to Study Product – By Decreasing Frequency – Includes Experiences of Any Relationship
- Expedited Adverse Experiences (EAEs) Reported to the Regulatory Support Center (RSC)/Serious Adverse Events (SAEs)

Additional tables included in the FSR for Safety:

- AESIs listing
- MAAEs listing
- Pregnancies listing
- HIV Acquisition Results from Lab and Reported by Site
- Study Product Administration Errors
- End of Study Diagnostic ELISA Testing Results
- Local Lab Value Summary Statistics
- Local Laboratory Values Meeting Grade 1 AE Criteria or Above

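### At interim SMB reviews, cumulative AE and reactogenicity percentages are not comparable between groups that have had different numbers of doses

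*SAP*

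**What the plan says.** SAP section 10.2 defines the AE summary: "The number and percentage of subjects experiencing each specific AE will be tabulated by severity and relationship to study vaccine". The counting rule is that "each subject's AE will be counted once under the maximum severity or strongest recorded causal relationship to treatment". Reactogenicity is handled alike: "each subject's reactogenicity will be counted once under the maximum severity for all assessments". Section 10 includes all enrolled participants whatever number of vaccinations they received. It is written for the final analysis and gives no separate rule for interim reports.

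Section 11.1 nevertheless introduces its main list with "The following tables are included in the SMB reports and FSR for safety", so the same AE and reactogenicity tables serve both purposes. That list also contains "Demographics and Study Product Administration Frequencies". No listed AE or reactogenicity table is specified by vaccination number, doses given or follow-up time.

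On timing, SAP section 5 states: "Enrollment in Groups 2, 3, and 4 will be stepwise by group, starting with Group 2", with Group 3 next and Group 4 last. Protocol section 9.6 reports the Part A third-dose safety review in the past tense, so Group 1 was well ahead when Part B was added. Each regimen has doses at months 0, 2, 4, 8 and 12 (Protocol section 7.1). The SMB meets about every 4 months (Protocol section 9.3.2).

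**The concern.** Unsolicited AEs are collected for 30 days after each vaccination (Protocol section 9.1), so the chance of ever having had one rises with every dose. The same holds for the worst reactogenicity grade so far. If one group has had four or five doses and another has had one, their ever/never percentages measure different things even at identical per-dose risk.

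Comparison between groups is intended. Protocol section 2.5 says that Part B should show whether the reactogenicity seen with 5 mcg 3M-052-AF plus Alum falls at 3 mcg, with Part A as comparator. SAP section 6 worries about events arising by chance more often in one arm than another, but its only remedy is the reported relationship to product. SAP section 7 urges caution because groups are not randomised. Neither section mentions unequal dosing. The stake is that a true excess in a newly opened regimen could look unremarkable in the SMB summary tables while vaccination continues.

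**Working it through.** **The plan's own figures.** The documents give no percentages by dose count. The nearest figures are the binomial probabilities in SAP Table 2-3, and these reproduce. For n = 12 and a 10% rate, P(0) = 0.9^12 = 0.28, P(1+) = 0.72 and P(2+) = 0.34, as printed. The score intervals in Table 2-4 also reproduce.

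**Inputs.** From the documents: five doses at months 0, 2, 4, 8 and 12; 12 participants per group; stepwise enrolment; SMB reviews about every 4 months. Assumed: constant per-dose risk p in the earlier group and 2p in the later group, independent doses, and tables split by group.

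**Expected percentage ever affected.** Earlier group after k doses: 1 − (1 − p)^k. Later group after m doses: 1 − (1 − 2p)^m. With p = 10%:

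| Doses received | 1 | 2 | 3 | 4 | 5 |
|---|---|---|---|---|---|
| Earlier group, 10% per dose | 10.0% | 19.0% | 27.1% | 34.4% | 41.0% |
| Later group, 20% per dose | 20.0% | 36.0% | 48.8% | 59.0% | 67.2% |

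- Near-equality: 19.0% v 20.0% at 2 v 1 doses, and 34.4% v 36.0% at 4 v 2.
- Reversal: 27.1% v 20.0% at 3 v 1, 34.4% v 20.0% at 4 v 1, 41.0% v 20.0% at 5 v 1, and 41.0% v 36.0% at 5 v 2.
- Correct order: 27.1% v 36.0% at 3 v 2, 41.0% v 48.8% at 5 v 3, and always at equal doses.

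**When reversal can occur.** (1 − p)² = 1 − 2p + p², which exceeds 1 − 2p. So the later group always has the higher expected percentage when k ≤ 2m. On a five-dose schedule this leaves four reversing pairs: 3 v 1 for p up to about 0.38, 4 v 1 up to 0.46, 5 v 1 up to 0.48, and 5 v 2 up to 0.28.

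**With 12 per group.** The probability that the riskier, later group shows the lower observed percentage is:

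| p | 5 v 1 doses | 5 v 2 doses | 5 v 3 doses | Same dose (1 v 1) |
|---|---|---|---|---|
| 2% | 0.54 | 0.41 | 0.31 | 0.14 |
| 5% | 0.72 | 0.49 | 0.31 | 0.18 |
| 10% | 0.82 | 0.52 | 0.28 | 0.16 |
| 20% | 0.88 | 0.48 | 0.20 | 0.09 |

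**How often reviews would be affected.** Assume p = 10%, accrual over up to 3 months and reviews every 4 months at all four monthly offsets. Count reviews held while the later group is still being vaccinated. Expected reversal occurs at none of 14 to 16 reviews if the groups start 1 to 3 months apart, 3 of 16 at 4 months, 5 of 16 at 6 to 8 months, and 6 of 16 at 12 to 18 months.

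**The case against.** The strongest reply is that the SMB does not depend on these percentages.

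- It sees doses given, in the product administration table.
- SAP section 11.2 gives it participant listings of severe reactogenicity, moderate erythema and induration, SAEs, AESIs, MAAEs, severe AEs and AEs by relationship to product. With about 12 people per group, these can be read case by case.
- The PSRT reviews safety weekly (Protocol section 9.3.1), the pause and prompt-review rules in Table 9-1 act on single related events, and "The SMB conducts additional special reviews at the request of the HVTN 300 PSRT".
- The stated safety goal is to identify concerns, not to rank groups, and the SAP does not state that SMB tables are split by group.

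Most of this stands, and it means that a serious signal is unlikely to be missed. It does not make the percentages comparable, because a count of doses cannot turn an ever/never percentage into a per-dose one.

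Three stronger readings are tempting, and the documents do not support them. A reader might infer that a later, riskier group will generally show the lower figure. That needs more than twice the doses in the earlier group, and a participant on schedule has had exactly one dose for only about two months. A reader might infer that a real excess would be hidden, but the listings and event-level rules contradict this. A reader might also calibrate the risk from HVTN 122, where "60% (n=27) of participants experienced one or more AEs". Only one of those AEs was judged related to product, and that trial used another immunogen with Alum and no 3M-052-AF, so the figure says little about vaccine-related risk here.

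**Conclusion.** The concern holds in a limited form. Cumulative percentages of participants are not comparable between groups at an interim SMB review when dose counts differ. Under the assumed 10% v 20% per-dose risks, a true doubling shrinks to one percentage point at 2 v 1 doses and reverses to 41.0% v 20.0% at 5 v 1.

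This is most plausible for Group 1 against a newly started Part B group. Between successive Part B groups it depends on an enrolment pace that the documents do not give; with gaps of 1 to 3 months the calendar check at p = 10% found no reversal. In the final report it largely disappears if all groups complete five doses. The per-dose risks, their constancy and independence, the gaps, the accrual times and the split of SMB tables by group are assumptions. Given the other safeguards, this is an inexpensive improvement that should be made, not a defect that leaves participants unmonitored.

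**What to change.** In SAP sections 10.2 and 11.1, add to the SMB reports AE-by-severity and maximum-reactogenicity tables by group and vaccination number.

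- **Denominator:** participants in the group who received dose k.
- **AE numerator:** those with an AE starting after dose k and before the earlier of 30 days or the next dose. The second limit is needed because the Appendix C windows allow dose 2 as late as day 56 + 14 = 70 and dose 3 as early as day 112 − 21 = 91, only 21 days apart.
- **Reactogenicity numerator:** those with the sign or symptom in the 7-day period after dose k, at its maximum grade in that period.

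Keep the cumulative tables in both the SMB and final reports. Protocol section 9.3.2 has the SMB review cumulative reactogenicity, and later-onset SAEs, AESIs and MAAEs fall outside a 30-day window.

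Compared at the same dose number, the expected percentages are p and 2p, so the order is right in expectation. Small numbers remain a limit: at 10% v 20% with 12 per group, the observed order is right with probability 0.66, tied 0.19 and reversed 0.16 (rounded). The tables should therefore be read descriptively. The cost is SAP wording, programming on data already collected, and more pages with cells of about 12 per group and dose.
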